9.6 IGF-1

The number and percentage of subjects will be presented where:

- IGF-1 SDS > 2.0
- IGF-1 SDS > 3.0

for at least 2 consecutive assessments.

Incidence of subjects with abnormally high IGF-1 SDS will be presented

9.7 Bone Age

The change in bone age, the ratio of bone age over chronological age, and the ratio of bone age advancement over chronological age advancement will be calculated. Subjects with too much bone age advancement will be reviewed for potential safety implications.

9.8 Injection site reactions (ISRs)

The number and percentage of subjects will be presented for ISRs and ISRs resulting in discontinuation.

9.9 Further Safety Evaluations

Results of physical examination will be summarized by treatment group, body system, and visit.

A data listing of physical examinations will also be provided, displaying details of each physical examination captured on the CRF.

Local tolerability will be summarized based on the investigator's and subject/parents/legal guardians assessment of pain, erythema, bruising, itching, and swelling.

A data listing of investigator's and subject/parents/legal guardian assessment will also be provided.

9.10 Concomitant Medication

Concomitant medications will be analyzed in the same way as prior medications.

Permitted Concomitant Medications

- Replacement therapy for pituitary deficiencies of other axes. As growth hormone may enhance the transformation of hydrocortisone to cortisone, the investigator may increase the dose of hydrocortisone replacement therapy if needed (eg, for anticipated stress).
- Glucocorticoid therapy for indications other than adrenal replacement (eg, asthma) may be administered in a dose equivalent to inhaled budesonide of not more than 400 µg/d for

a maximum of approximately 1 month during 1 calendar year (approximate equivalent doses: fluticasone: 264 µg/d; beclomethasone: 504 µg/d; flunisolide 1,000 µg/d; triamcinolone: 1,000 µg/d; mometasone: 211 µg/d; ciclesonide 264 µg/d).

- Treatment for diabetes
- Over-the-counter vitamins, minerals or other dietary supplements only if their use is agreed to by the investigator.

Prohibited Concomitant Medications

- Estrogen
- Anabolic steroids; systemic corticosteroids other than in the doses indicated above
- Weight-reducing drugs or appetite suppressants other than for the treatment of ADHD

A concomitant medication is defined as any medication other than the investigational or reference product that is administered from the first day of study drug administration up until the end of the trial. The frequency and percentage of all concomitant medications will be summarized by ATC class 2 and ATC class 4 if applicable for all safety subjects in the study population by treatment group, unless otherwise specified.

If the start/stop dates of a medication are partially or completely missing, then the medication will be assumed to be concomitant if it cannot be definitely shown that it was not administered during the treatment period. Missing dates will not be replaced.

Thus, the following approach will be taken for exclusion from concomitant medications because of discontinuation before start of treatment:

If the stop day is missing but the month is complete, then the medication will be excluded from concomitant medications only if the stop month is before the month of treatment start.

If the stop day and month are missing but the year is complete, then the medication will be excluded from concomitant medications only if the stop year is before the year of treatment start.

If the stop date is completely missing, then the medication will not be excluded.

9.11 Exposure and Compliance

For each subject, the individual extent of exposure will be calculated in terms of:

- Total duration of treatment
- Total number of planned doses
- Total number of actual doses
- Actual Total dosage (mg)

These variables will be listed by subject, sorted by treatment group and subject number. Summary statistics per treatment group will be tabulated overall.

For the TransCon hGH group, subjects whose weekly actual dosage (mg/kg/wk) differ from the planned weekly dosage of 0.24 mg/kg/wk will be identified and followed for potential explanation.

Study drug compliance will be calculated as:

Total number of doses taken /total number of planned doses

Compliance will be summarized using the following categorization; <80%, ≥80%, ≥90%, ≥95% and ≥100%

Exposure and compliance will be listed by subject and presented for the safety population set by means of summary statistics by treatment group.

10. Changes from Planned Analysis

No changes from planned analysis.

11. Other Planned Analyses

11.1 Pharmacokinetic and Pharmacodynamic Analyses

11.1.1 Safety Population Exposure Data, PK analytes

Blood samples will be processed to serum for quantitation of hGH, TransCon hGH (ie, TransCon PEG40 hGH) and PEG (measured as total methoxypolyethylene glycol, 40 KDa [mPEG40]), at Screening and Visit 1 through Visit 6. The samples will be analyzed according to [Table 4](#) below.

Table 4: Blood Sampling Process

Cohort 1	Analyte	Screening	Visit 1 Week 1	Visit 2 Week 5	Visit 3 Week 13	Visit 4 Week 26	Visit 5 Week 39	Visit 6 Week 52
(TransCon hGH)		-	Predose	Predose	48-72h post dose	48-72h post dose	48-72h post dose	168h post dose
	hGH	x	x	x	x	x	x	x
	TransCon hGH	-	x	x	x	x	x	x
	PEG	x	x	x	x	x	x	x
Cohort 2		Screening	Visit 1	Visit 2	Visit 3	Visit 4	Visit 5	Visit 6
(Genotropin)		-	Predose, 2h	Morning	Morning	Morning	Morning	Morning
	hGH	x	x	x	x	x	x	x
	PEG	x	x ¹	-	-	-	-	-

¹Predose only

The lower limits of quantitation (LLOQ) for each of the PK analytes are as follows:

- hGH: 2.00 ng/mL
- TransCon hGH: 20.0 ng hGH/mL
- Total PEG: 300 ng/mL

Serum concentration values below the limit of quantification (BLQ) will be set to zero when calculating summary statistics. Serum concentration data will be listed and summarized by nominal visit/timepoint for each Treatment and analyte using descriptive statistics. For serum concentration listings, three significant figures will be reported as in the original serum concentration raw data.

Arithmetic mean and individual serum concentration data versus visit will be presented in figures.

Accumulation ratios will be calculated for TransCon hGH, PEG and hGH, where possible and as data permit.

11.1.2 PK/PD-subset Sample Concentration Data, PK analytes

Blood samples for PK assessment in TransCon hGH Cohort 1 PK/PD Population will be collected at Visit 3 (Week 13) at following time points: Predose (defined as time zero), 8, 12, 16, 24, 36, 48, 72, 96, 120 and 168 hours post dose.

Below are the time windows by design for PK sample collection:

- Cohort 1: Predose (-0.5 hour): within \pm 30 minutes
- Cohort 1: 8 to 48 hours post-dose: \pm 1 hour
- Cohort 1: 72 to 168 hours post-dose: \pm 3 hours

All concentrations will be included in the PK analysis using actual times post-dose. Blood samples will be processed to serum for quantitation of hGH, TransCon hGH and PEG. Arithmetic mean serum concentration versus nominal time profiles will be presented in figures on both linear and semi-logarithmic scales for the PK/PD subset. Individual serum concentration versus actual time profiles will be presented in figures on both linear and semi-logarithmic scales.

11.1.2.1 Pharmacokinetic Parameters

Pharmacokinetic parameters will be calculated for the following analytes:

- hGH
- TransCon PEG40 hGH
- mPEG40

The individual serum concentration versus actual time data for all analytes will be used to derive the PK parameters using non-compartmental analysis, as deemed appropriate, using Phoenix WinNonlin (Version 6.4 or higher).

The following serum PK parameters will be estimated for each analyte. Other parameters may be calculated if deemed necessary and as data permit.

Parameter	Description
C _{max}	Maximum observed serum concentration
C _{max} /dose	Maximum observed serum concentration divided by dose
T _{max}	Time to reach maximum observed serum concentration
T _{last}	Time of the last quantifiable concentration
AUC _{0-t}	Area under the serum concentration-time curve from time 0 to the last quantifiable concentration calculated by the linear trapezoidal rule: $AUC_{0-t} = \sum_{i=1}^n \frac{(C_i + C_{i-1})}{2} (t_i - t_{i-1})$, where C _i and C _{i-1} is the serum or plasma concentration at t _i and t _{i-1} , respectively, and t _i -t _{i-1} is the time interval.
AUC ₀₋₁₆₈	Area under the serum concentration-time curve from time 0 to 168 hours
AUC/dose	Area under the serum concentration-time curve divided by dose
k _{el}	Terminal phase rate constant, calculated using linear regression on the terminal portion of the ln-concentration versus time curve. At least 3 time points (excluding C _{max}) and adjusted r ² ≥ 0.80 are required to calculate and retain k _{el} and its associated parameters.
t _{1/2}	Terminal elimination half-life, calculated as t _{1/2} = ln(2)/ k _{el}
r ²	Correlation coefficient (goodness of fit statistic) associated with the estimation of k _{el}
V _Z /F	Apparent volume of distribution, calculated as V _Z = Dose / k _{el} x AUC _{0-inf}
CL/F	Apparent Clearance, calculated as Cl = Dose/ AUC _{0-inf}

For serum concentration data, all values below the limit of quantification (BLQ) will be set to 0 for summary statistics and graphs. For the calculation of the PK parameters, serum concentrations that are BLQ will be set to 0 before T_{max}, with the exception of a BLQ value occurring between measurable concentrations, in which case it will be set to missing. All values that are BLQ will be set to missing after T_{max}.

Actual sampling times will be used to calculate the PK parameters. The individual PK parameters for hGH, TransCon PEG40 hGH and mPEG40 will be presented in a data table. Pharmacokinetic parameters will be summarized using descriptive statistics (number of subjects, arithmetic mean, 95% CI of arithmetic mean, geometric mean, arithmetic SD, arithmetic CV, geo

CV, median, minimum, and maximum). For T_{max} and T_{last} , only the range and the median will be reported. For the display of PK parameters in tables, the PK parameters and descriptive statistics will be presented with 3 significant figures.

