Literature data indicate that the PEG associated with a biological molecule should provide no extra concern because the exposure-toxicity relationship of PEG in animals and humans has been well investigated and metabolism/excretion of PEG is well understood, indicating that the PEG associated with a biological molecule does not represent an unacceptable additional risk to humans ([Webster 2007](#)). Detailed information is given in the Investigator's Brochure.

5.3.1 Pharmacokinetics of hGH Following Administration of TransCon hGH (ACP-001) and TransCon hGH (ACP-011)

This was a phase 1 single center, randomized, open label trial to evaluate the safety, tolerability, pharmacokinetics, and pharmacodynamics of ACP-011 at doses of 0.24, 0.30, and 0.42 mg hGH/kg administered subcutaneously to healthy subjects. There was a crossover portion to the trial to compare the PD parameters of ACP-011 and ACP-001 at the 0.24 mg hGH/kg dose level.

TransCon hGH (ACP-011) was found to be bioequivalent to TransCon hGH (ACP-001), with the ratios of the means for C_{max} and AUC for both released hGH and IGF-1 falling within the bioequivalence limits of 80 % – 125%. Following a single subcutaneous administration of TransCon hGH (ACP-011), free hGH showed a dose dependent increase in mean serum C_{max} and AUC within the dose range 0.24 to 0.42 mg hGH/kg. Serum concentrations increased rapidly with a median time to maximum concentration is attained (T_{max}) of 16.0 to 36.0 hours, indicative of release of hGH from TransCon hGH in both the subcutaneous tissue and the systemic circulation. Elimination appeared in a mono-phasic manner and the mean terminal half-life ranged from 21.8 to 25.4 hours independent of dose. TransCon hGH (ACP-001) dosed at 0.24 mg hGH/kg exhibited comparable T_{max} , C_{max} and AUC_{0-168h} for hGH and IGF-1 to the equivalent dose of TransCon hGH (ACP-011).

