9.3. Treatments Administered

9.3.1 TransCon hGH

TransCon hGH will be provided as a lyophilized powder, in single-use glass vials, to be reconstituted with 1 mL sterile water for injection. For the composition and characteristics of TransCon hGH, refer to the Investigator's Brochure.

TransCon hGH will be injected SC into the left and right buttock, left and right thigh, and left and right abdomen in the morning hours by the trial staff or by the subject/parent/legal guardian. To minimize local side effects it is recommended to rotate the 6 injection sites in a subsequent manner (eg, right buttock, right abdomen, right thigh, left thigh, left abdomen, left buttock).

During the extension trial planned at the conclusion of this 52-week randomized trial, the plan is to switch from TransCon hGH (ACP-011) in vials to TransCon hGH (ACP-011) in dual chamber cartridges (DCC's), in which TransCon hGH will be supplied as a single dose in a DCC for administration by an Auto-Injector. The DCC presentations will use the 2 compounded solution concentrations also used for the vials in the randomized portion of this trial, 12.1 mg hGH/vial (11.0 mg hGH/mL when reconstituted) and 24.2 mg hGH/vial (22.0 mg hGH/mL when reconstituted), and will be filled with different volumes of the 2 solutions to provide nine presentations with dose increments of approximately 20%. Doses from 3.0 mg hGH to 13.3 mg hGH will be available. When the subjects are dosed with 0.24 ± 0.02 mg hGH/kg/week the associated volumes for injection for each weight range are shown in the table below (Table 1).

For the trial to support the use of the Auto-Injector during the extension phase, the aim is to mimic the dose increments and the associated weight ranges both with respect to injection volume and mg hGH. Therefore, 2 vial presentations will be manufactured; a 12.1 mg hGH/vial (11.0 mg hGH/mL when reconstituted) and 24.2 mg hGH/vial (22.0 mg hGH/mL when reconstituted). Only the drug product at 12.1 mg hGH/vial will be available at start of phase 3. The consequence is that subjects ≥ 24 kg will initially be dosed with a somewhat higher volume, and subjects ≥ 42 kg will initially need 2 injections on the same day using 2 different injection site locations until the 24.2 mg hGH/vial is available during resupply of study drug.

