- 8) Auxology measurements (actual height and body weight), to be performed by the same, trained, blinded (if possible) auxologist at approximately the same time of day (morning) at each visit if possible
- 9) Fundoscopy (at V4 and V6, and at other visits if clinically indicated)
- 10) Pubertal status assessment (at V4 and V6)
- 11) Training on study drug preparation and administration (V1 - during first administration and further as needed)
- 12) Study drug administration at site at Visit 1 (both cohorts) and Visit 2 (TransCon hGH cohort only) (dose should be adjusted at V3, V4 and V5 according to the subject's weight) – by the trial staff or subject/parent/legal guardian
- 13) Vital signs will be assessed over 2 hours at Visit 1, at every clinic visit for all subjects, including over 24 hours postdose at V3 for the Cohort 1 PK/PD subset (subjects should rest for at least 5 minutes before vital sign assessment)
- 14) ECG at V1 and V4 for all subjects; additionally at V3 only in PK/PD subset at predose and 8, 12, 16, 24, 36, 48, 72, 96, 120 and 168h postdose for TransCon hGH subjects (subjects should rest for at least 2 minutes before ECG assessment)
- 15) Bone age at V6

The dose of TransCon hGH or Genotropin initially administered will be calculated using the weight measurement obtained at Visit 1 (predose). The dose of TransCon hGH or Genotropin will be adjusted according to the subject's weight measurement at Visit 3 (prior to dosing for the PK/PD subset), Visit 4, and Visit 5.

At each visit the parents/legal guardians will be given enough study drug for treatment until the next visit. Subject Diary availability will be ensured to record the date and time of injection, any local reactions or other Adverse Events and concomitant medication.

It is suggested that the site staff follows up with the subject between the visits by eg, phone calls.

Table 2
Bioanalytical Samples at Visits 1 to 6

Visit	Time Relative to Dosing, by Visits (Hours)					
	1	2	3	4	5	6
TransCon hGH	predose, morning	predose, morning	48-72h, morning	48-72h, morning	48-72h, morning	164-172h, morning
Week	1	5	13 (+2)	26 (±1)	39 (±1)	52 (+1)
Day	1	29	87-88	178-179	269-270	365
Genotropin	predose, 2h, morning	morning	morning	morning	morning	morning
Week	1	5	13 (+2)	26 (±1)	39 (±1)	52 (+1)
Day	1	29-35	85-91	176-182	267-273	365

h=hours; hGH = human growth hormone

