10.1.2.3 Pharmacokinetic/Pharmacodynamic Subset

At least 8 subjects from selected sites and countries in Cohort 1 will be assessed in a PK/PD subset analysis. Subjects will attend Visit 3 on Day 1 of Week 13 (Day 85). Visit 3 may be performed within a window of + 2 weeks, starting on Day 1 of either Week 13, 14 or 15. Subjects will stay at the hospital or come back for the scheduled procedures to assess safety and PK/PD profile over 1 week and ECGs intended to bracket presumed C_{\max} of hGH, IGF-1, and TransCon hGH prodrug:

- Blood sampling for PK (TransCon hGH, hGH, and PEG levels): predose (at -0.5h) and at 8, 12, 16, 24, 36, 48, 72, 96, 120 and 168 hours (h) relative to the 13th TransCon hGH dosing
- Blood sampling for PD (IGF-1 and IGFBP-3 levels): predose (at -0.5h) and 8, 12, 16, 24, 36, 48, 72, 96, 120, and 168 h relative to the 13th TransCon hGH dosing
- ECG measurements will be done predose and at 8, 12, 16, 24, 36, 48, 72, 96, 120 and 168 h postdose
- Vital signs and injection site evaluations will be done at 15 min, 1h, 2h, and 24h postdose
- The 14th dose injection will be given at the clinic

For subjects in the PK/PD subset, all other procedures planned for Visit 3 are also to be performed on the Day 1 of the respective week, prior to dosing. The subject and parents/legal guardians may be offered accommodation until all assessments are completed and the 14th dose given, depending on the agreement of the investigator with the parents/legal guardians, to ensure comfort for the child and reduce unnecessary travel.

Each PK/PD blood sample will require 2 mL of blood (details in [Appendix 5](#)).

The collection, processing, storage, and shipment of samples are described in the Laboratory Manual.

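### SAP 11.1.2.1 computes CL/F and Vz/F from AUC0-inf, a single-dose formula, on a profile taken after the 13th weekly dose, so CL/F is biased low

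*SAP*

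**What the plan says.** The parameter table in SAP 11.1.2.1 applies to three analytes: hGH, TransCon PEG40 hGH (the prodrug) and mPEG40. It gives CL/F as "Apparent Clearance, calculated as Cl = Dose" divided by AUC0-inf. The Vz/F row begins "Apparent volume of distribution, calculated as" and continues with dose, k_el and AUC0-inf on one line without brackets. AUC0-inf has no row of its own in the table. AUC0-168 has one, but neither formula uses it.

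The data come from one occasion. SAP 11.1.2 states: "Blood samples for PK assessment in TransCon hGH Cohort 1 PK/PD Population will be collected at Visit 3 (Week 13". Protocol 10.1.2.3 fixes the sampling times, ending with "120 and 168 hours (h) relative to the 13th TransCon hGH dosing".

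The SAP elsewhere recognises that drug may carry over. Section 11.1.1 plans accumulation ratios for all three analytes, and section 8.3 treats visits 3 to 6 as steady state (written there for IGF-1 sampling). Subtraction of a baseline appears only for IGF-1 and IGFBP-3, in section 11.1.3.

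**The concern.** Dose/AUC0-inf equals CL/F only when all the drug under the curve came from the dose in the numerator. After 13 weekly doses the curve also holds what remains of doses 1 to 12, and extrapolating it to infinity counts that drug against one dose. The denominator is too large and CL/F too small. The slower the clearance, the larger the error.

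Vz/F carries the same factor, but its net direction also depends on how well k_el is estimated.

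At stake are two reported rows for each of three analytes. SAP 11.1.2.1 summarises the parameters with means and 95% confidence intervals to three significant figures. Such an interval does not cover a systematic error.

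**Working it through.** The documents state no CL/F or Vz/F value, so there is no figure to reproduce. The check superposes 13 equal weekly doses under linear kinetics and divides the CL/F the formula would report by the true CL/F.

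**Inputs**

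- Dosing interval: 168 h; profile after dose 13 (Protocol 10.1.2.3).
- hGH half-life: "the mean terminal half-life ranged from 21.8 to 25.4 hours independent of dose" (Protocol 5.3.1).
- hGH median Tmax: "of 16.0 to 36.0 hours, indicative of release of hGH from TransCon hGH" (Protocol 5.3.1). Both hGH inputs come from single doses in healthy subjects.
- PEG and prodrug half-lives: not given. Assumed range 48 to 336 h.

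**Step 1. Mono-exponential decline, instant input.** Let e = 2^(−168/t½), with dose = 1 and true CL/F = 1.

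- AUC0-inf after dose 13 = (1 − e^13)/(1 − e), so Dose/AUC0-inf = (1 − e)/(1 − e^13).
- AUC0-168 after dose 13 = 1 − e^13, so Dose/AUC0-168 = 1/(1 − e^13).

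| t½ (h) | e | Dose/AUC0-inf | Dose/AUC0-168 |
|---|---|---|---|
| 21.8 (hGH) | 0.005 | 0.995 | 1.000 |
| 25.4 (hGH) | 0.010 | 0.990 | 1.000 |
| 48 (assumed) | 0.088 | 0.912 | 1.000 |
| 72 (assumed) | 0.198 | 0.802 | 1.000 |
| 96 (assumed) | 0.297 | 0.703 | 1.000 |
| 168 (assumed) | 0.500 | 0.500 | 1.000 |
| 336 (assumed) | 0.707 | 0.296 | 1.011 |

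**Step 2. hGH with first-order input.** Input rate ka is solved from Tmax = ln(ka/k)/(ka − k), with k = ln 2/t½. The exact column integrates the curve to infinity. The last two columns mimic the planned analysis: SAP sampling times, linear trapezoid, and k_el from the last three points.

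| t½ / Tmax (h) | Dose/AUC0-inf, exact | Dose/AUC0-inf, as sampled | Dose/AUC0-168, as sampled |
|---|---|---|---|
| 21.8 / 16 | 0.993 | 0.992 | 0.999 |
| 21.8 / 24 | 0.988 | 0.982 | 0.994 |
| 25.4 / 16 | 0.987 | 0.986 | 1.000 |
| 25.4 / 24 | 0.982 | 0.976 | 0.995 |
| 25.4 / 36 | 0.949 | 0.939 | 0.997 |

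A Tmax of 36 h cannot occur with a 21.8 h half-life in this model, because Tmax must stay below 1/k = 21.8/0.693 = 31.5 h. At that limit the exact ratio is 0.970.

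**Step 3. Vz/F.** Its ratio is the CL/F ratio times estimated t½ over true t½. In the 25.4/36 row the last three points give a half-life of 34.3 h, so Vz/F is 0.939 × 34.3/25.4 = 1.27, which is too high. In the 25.4/16 row the half-life is recovered, and Vz/F is low by the same 1.4% as CL/F. Hence no single direction for Vz/F.

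**Step 4. Slow analyte with an assumed single-dose Tmax of 36 h.** The exact Dose/AUC0-inf ratios at 48, 72, 96, 168 and 336 h are 0.878, 0.773, 0.680, 0.488 and 0.292, slightly worse than Step 1.

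**Step 5. Dose changed at the profile.** Protocol 10.1.2 re-sets the dose by "weight measurement at Visit 3 (prior to dosing for the PK/PD subset", so dose 13 may differ from doses 1 to 12. Protocol 9.3.1 describes increments of about 20% for the cartridges and says of the vials that "the aim is to mimic the dose increments and the associated weight ranges"; the steps in Table 1 compute to 17–23%. With dose 13 = 1.2 and earlier doses = 1:

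- Dose/AUC0-168 = 1.2/(1.2 − 0.2e − e^13).
- Dose/AUC0-inf = 1.2/(1.2 + e(1 − e^12)/(1 − e)).

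| Assumed t½ (h) | Dose/AUC0-168 | Dose/AUC0-inf |
|---|---|---|
| 48 | 1.015 | 0.925 |
| 72 | 1.034 | 0.829 |
| 96 | 1.052 | 0.739 |
| 168 | 1.091 | 0.546 |
| 336 | 1.146 | 0.336 |

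**The case against.** **The rows matter little.** CL/F and Vz/F are not among the PK endpoints in SAP 2.2.3, and they feed no test or dosing rule. With 8 subjects and an assumed between-subject CV of 30%, the 95% interval on a mean is about ±25% (2.365 × 30%/√8), far wider than the hGH error. This stands and limits the consequence. It does not make the formula fit the design.

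**The 6% for hGH is an extreme.** It needs the longest half-life with the latest Tmax, a pairing the Protocol does not state. The other four pairs, as sampled, give 0.8–2.4%. This stands.

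**The large errors rest on assumed half-lives and on flat profiles that the k_el rule (at least 3 points, adjusted r² ≥ 0.80) would often reject.** In simulation with 10% assay noise and Tmax 36 h, both assumed, roughly 30% of profiles fail at a 168 h half-life and 65% at 336 h. So fewer CL/F values would be reported there, but those retained are still wrong. At 48–96 h most profiles pass.

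**AUC0-168 may not be fully observed for hGH.** Values below 2.00 ng/mL after Tmax are set to missing. In four of the five model pairs the 168 h level is 1.1–3.5% of Cmax, so it is quantifiable only if Cmax exceeds about 57–180 ng/mL (2.00/0.035 to 2.00/0.011). No Cmax is given. The point is fair, but AUC0-168 is already planned and faces it regardless.

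**The missing brackets may be layout only.** A volume cannot result from multiplying by AUC, so the intended meaning is clear. This is a minor correction.

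**Latitude in the SAP.** It allows non-compartmental analysis as judged suitable, and readers could rebuild Dose/AUC0-168 from reported values. The printed formula is still the specified one.

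**Conclusion.** The concern holds. As written, SAP 11.1.2.1 gives CL/F biased low for all three analytes.

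- **hGH:** about 1–6% low, most input pairs 1–3%, and 0.5–1.0% under mono-exponential decline with instant input. This assumes that single-dose values from healthy subjects carry over to these children.
- **PEG and prodrug:** size unknown, because no half-life is documented. It would be 9% to 70% low over assumed half-lives of 48 to 336 h, or 12% to 71% with an assumed Tmax of 36 h.
- **Vz/F:** same factor from AUC0-inf, with net direction depending on k_el.

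All figures assume linear kinetics and, except in Step 5, equal doses. The one-week profiles, hGH Cmax, k_el, t½, AUC0-168 and accumulation ratios do not use AUC0-inf. The formulas should be corrected, but no efficacy or safety conclusion depends on them.

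**What to change.** For the Week 13 profile, define CL/F = Dose/AUC0-168 and Vz/F = Dose/(k_el × AUC0-168), with the brackets written out, and remove AUC0-inf from both. Flag subjects whose dose changed at Visit 3, or report both parameters with and without them.

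The cost is two formula edits and one flag or footnote; there is no new sampling, and AUC0-168 is already planned. A sentence on how AUC0-168 is obtained when the 168 h sample is below quantification would also help.

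One limit remains. In a child who moved up one dose bracket at Visit 3, the new CL/F is about 1.5% to 15% too high over assumed half-lives of 48 to 336 h. In the same child the present formula would be about 8% to 66% too low.
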